## NORIG Trial Protocol

# 6. Statistical design and analysis

---

## 6.1 Hypotheses

### Primary hypothesis:

- Treatment with nortriptyline, compared to treatment with placebo, will result in a sustained reduction in Gastroparesis Cardinal Symptom Index (GCSI) score of 50% or greater from baseline in patients with idiopathic gastroparesis.

### Secondary hypotheses:

- Pharmacogenetic profiles of patients with idiopathic gastroparesis will identify subgroups of patients with differential response to nortriptyline, compared to placebo.
- Subgroups of patients with higher blood levels of nortriptyline during follow-up will experience a better response compared to placebo and compared to patients with lower blood levels of nortriptyline.
- Patients in the nortriptyline group will have improved satiety testing, but no change in electrogastrography compared to placebo.
- Treatment with nortriptyline will result in improved global overall relief of symptoms and Clinical Global Patient Impression (CGPI) compared to placebo.
- Patients in the nortriptyline group will have improvements in standardized quality of life scores, compared to placebo.
- A dose escalation strategy can be successfully used to optimize the dose of nortriptyline to maximize clinical benefit and reduce side effects.

## 6.2 Outcome measures

### Primary outcome measure:

The primary outcome measure is defined as a decrease from the baseline GCSI score (sum of the 9 individual symptom scores) of at least 50% on any two consecutive follow-up visits during the 15 week treatment period with maximum tolerated study drug dose. A sensitivity analysis will compare cumulative GCSI symptom scores averaged across all follow-up visits to rule out the possibility that an effect present in the primary analysis was due to the GCSI score decreasing 50% on two consecutive visits with smaller improvement or worsening on other follow-up visits.

All patients will be followed for the full 18 weeks after randomization regardless of response or

course of treatment to permit an intention-to-treat primary analysis.

The GCSI total score ranges from 0 to 45 (highest severity) and is calculated as the sum of nine individual symptom scores:

$$\begin{aligned} \text{GCSI} = & \text{Nausea (0-5) +} \\ & \text{Retching (0-5) +} \\ & \text{Vomiting (0-5) +} \\ & \text{Stomach fullness (0-5) +} \\ & \text{Not able to finish a normal sized meal (0-5) +} \\ & \text{Feeling excessively full after meals (0-5) +} \\ & \text{Loss of appetite (0-5) +} \\ & \text{Bloating (0-5) +} \\ & \text{Stomach visibly larger (0-5)} \end{aligned}$$

As noted earlier, a GCSI score of 21 or greater is a requirement for enrollment into the trial. The primary outcome measure is a binary (0, 1) variable, which equals to 1, if a GCSI score reduction of 50% or greater, relative to the baseline score, is observed on at least two consecutive follow-up visits during the 15 weeks of treatment and follow-up.

**Secondary outcome measures** will be defined to address the following areas:

- (1) Symptoms
  - Subscores for the GCSI such as nausea/vomiting, postprandial fullness, bloating
  - Individual symptom scores
  - Global overall relief of symptom questionnaire
  - Clinical global patient impression
- (2) Physiology
  - Satiety test: Volume of Ensure® consumed during satiety testing
  - Electrogastrography: Percent time in EGG dysrhythmias (outside 2.5-3.75 cycles per minute)
  - Side effects to treatment requiring stopping medication

**Subgroup differences** in response to nortriptyline will be addressed:

- (1) Differential response to nortriptyline based on pharmacogenetic analysis of patients
- (2) Differential response to nortriptyline based on blood levels of nortriptyline

### 6.3 Statistical analysis

The primary analysis will be made on “intention to treat” basis, which means that all randomized patients with GCSI scores at baseline and at any time during 15 weeks of treatment will be analyzed in the treatment group to which they were assigned. Any randomized patient who does not have the requisite GCSI scores will be treated as a non-responder and compared by assigned treatment group. Primary comparisons will be of the full nortriptyline group versus the full placebo group. Secondary, sensitivity analyses on a per-protocol basis will also be carried out, excluding patients from both groups who do not complete at least 60% (9 weeks) of the 15 weeks on assigned treatment.

Since the primary outcome measure is a binary indicator of improvement in GCSI score and since the randomization is stratified by clinic, P-values will be derived from the Mantel-Haenszel  $\chi^2$  test for stratified 2x2 tables, with stratification by clinic, comparing proportions improved in the group assigned to nortriptyline compared to the group assigned to placebo. The P-values so derived will be reported in the primary paper on the results of the trial. A P-value of 0.05 will be considered statistically significant.

Given the randomized design and adequate size planned for the NORIG trial, it is unlikely that confounding of the treatment groups by covariates related to the change in GCSI score will occur. However, if confounding should occur, sensitivity analyses using logistic regression models with GCSI score improvement as the binary response and treatment group indicator and any suspected confounders as covariates will be carried out to determine the sensitivity of the primary P-value to confounding; however, the Mantel-Haenszel derived P-value will be the primary P-value reported.

The first two secondary hypotheses listed above relate to differential effects of treatment in subgroups of patients defined by pharmacogenetic profiles and adherence levels (nortriptyline blood levels), respectively. The profiles and blood level cut offs will not be pre-defined, but will be made on the basis of the best available information at the time of analysis. To assess whether differential effects are present, a logistic regression model for the primary outcome with random effects for clinic and fixed effects for treatment group, subgroup indicator variables, and treatment group by subgroup interaction effects will be used. The evidence for differential subgroup effects will be considered statistically significant if the P-value for the interaction terms is <0.01.

Analyses related to the other secondary hypotheses (excluding the dose-escalation hypothesis, which will be addressed empirically) will be conducted in two ways. Improvement will be analyzed both as a binary outcome (improved vs. not improved) and also in terms of the numerical change in the outcome. Binary outcomes will be compared using the Mantel-Haenszel  $\chi^2$  test for stratified 2x2 tables. Numerical changes will be analyzed by descriptively comparing the between-treatment group differences in mean and median changes; P-values will be derived from Wilcoxon rank sum tests for comparison of the distribution of changes in each group. If concerns about confounding arise, logistic regression models for improvement outcomes and linear regression models for numerical change outcomes will be used to correct for the confounding. No adjustments for multiple comparisons will be applied to the secondary hypotheses, which are pre-specified; however, any significant findings will be interpreted cautiously, taking into account the strength of the finding and its biologic plausibility.

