**Sample size justification**

- Total of 130 patients in 2 groups of equal size (65 per group)
- Primary comparison: nortriptyline vs. placebo
- Error protection: Type I = 0.05 and Type II = 0.10 (90% power)
- Minimum clinically important difference (MCID): 50% reduction in GCSI outcome (see below) during 15 weeks of treatment
  - Expected percent with improved GCSI in the placebo group: 30%
  - Expected percent with improved GCSI in the nortriptyline group: 60%
  - Source of estimates of MCID: Consensus of GpCRC clinicians
- Statistical test and sample size software
  - Chi-squared test for two proportions
  - Dupont and Plummer PS software

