### 6.5 Justification of sample size

The planned sample size for the NORIG trial is 130 patients with equal allocation to each of the two treatment groups (65 per group).

We based the sample size estimates on a two-group, binomial comparison of the proportions of patients satisfying the primary outcome, improvement in the GCSI score over the course of treatment. For sample size purposes, the expected proportions improved (0.6 in the nortriptyline group compared to 0.3 in the placebo group), were derived from the expert opinions of clinicians on the GpCRC Steering Committee, based on their experience with the GCSI in patients with idiopathic gastroparesis similar to those meeting the eligibility criteria for the trial. The size of the smallest clinically meaningful effect (0.60 vs 0.30 response rates) was also based on the expert opinion of Steering Committee, taking into account the expected missing data rate of 10% and its consequent reduction in improvement rates.

The sample calculations were performed using the nQuery Advisor 5.0^33 software, which uses the formula:

$$n = \frac{\left[ z_{1-\alpha/2} \sqrt{2\bar{\pi}(1-\bar{\pi})} + z_{1-\beta} \sqrt{\pi_1(1-\pi_1) + \pi_2(1-\pi_2)} \right]^2}{(\pi_1 - \pi_2)^2}$$

where,

$n$  = sample size per group

$\pi_1$  = expected proportion with 50% improved GCSI in placebo group (assumed=0.30)

$\pi_2$  = expected proportion with 50% improved GCSI in nortriptyline group (0.60)

$\bar{\pi}$  = average of  $\pi_1$  and  $\pi_2$

$\alpha$  = Two-sided type I error (0.05)

$\beta$  = Type II error (0.10; i.e., 90% power)

The number per group, using the above formula is 56 for a total of 112. To allow for possible mis-specification in the estimated response rates used in the calculation, we propose a sample size of 65 patients per group, or a total of 130 for the trial.

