### 6.6 Interim analysis

An independent Data and Safety Monitoring Board (DSMB), appointed by the NIDDK, is responsible for approving the protocol for the NORIG trial and for monitoring the accumulated interim data as the trial progresses to ensure patient safety and to review efficacy. The DSMB is a multi-disciplinary group with a written charge provided by the NIDDK. The DSMB reports to the NIDDK, which will, in turn, communicate DSMB recommendations to the investigators, as appropriate.

The DSMB meets to approve the protocol. After the trial commences, the DSMB meets twice a year to review data or other issues. The DSMB may request more frequent meetings if necessary to fulfill its charge. It may also request additional safety reports on a more frequent basis.

Interim data on safety measures requested by the DSMB are reviewed at each of the scheduled semi-annual full meetings. Two additional written safety reports will be reviewed by the DSMB between scheduled full meetings. Serious adverse events will be reviewed by the DSMB as they occur with the option of a teleconference discussion if any DSMB member so requests.

The DSMB reviews one planned interim analysis of the primary outcome measure. O'Brien-Fleming statistical stopping guidelines for efficacy apply. This interim efficacy analysis will occur when approximately 50% of the data are complete or when approximately 65 of the 130 patients have completed the 18 week trial. The interim monitoring bounds were adjusted for one interim look as follows: We propose guidelines (boundaries) with O'Brien-Fleming Type 1 error spending functions for the primary outcome.

The DSMB also reviews the overall progress of the trial in terms of recruitment and data quality and makes a formal recommendation to the NIDDK at the end of each scheduled meeting as to whether the trial should continue unmodified, continue with protocol modifications, or be stopped.

---

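### The 0.05 threshold for the primary P-value in section 6.3 is not reconciled with the O'Brien-Fleming efficacy look in section 6.6

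*Protocol*

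**What the plan says.** - **Overall error.** The design synopsis (sample size justification) sets the Type I error at 0.05, and section 6.5 makes it two-sided. Neither mentions a split between looks.
- **Threshold for the primary test.** Section 6.3 takes the primary P-value from the clinic-stratified Mantel-Haenszel test, makes it the one reported in the primary paper, and adds: "A P-value of 0.05 will be considered statistically significant". It does not mention the interim analysis.
- **Interim look.** Section 6.6 states: "The DSMB reviews one planned interim analysis of the primary outcome measure". The look comes at about 50% of the data, roughly 65 of 130 patients, under O'Brien-Fleming guidelines for efficacy.
- **Bounds.** Section 6.6 continues: "The interim monitoring bounds were adjusted for one interim look as follows". What follows names only the family, O'Brien-Fleming error-spending functions for the primary outcome. There is no critical value or nominal level for either look.

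**The concern.** If an efficacy claim can be made at the halfway look, part of the 5% error is used there, and the final analysis must use a threshold slightly below 0.05 to keep the total at 5%. The only number the protocol gives for judging the primary P-value is 0.05. An analyst who follows section 6.3 as written would use it at the end; one who follows section 6.6 would use a lower value.

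This is the single primary comparison of a Phase III trial. A final P in the narrow band between the two thresholds would be significant by section 6.3 and not significant by section 6.6, and the protocol does not say which section governs.

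**Working it through.** **Inputs from the protocol.** Two-sided Type I error 0.05, power 0.90, response 0.30 on placebo and 0.60 on nortriptyline, 65 per group (section 6.5); one efficacy look at information fraction t = 0.5, O'Brien-Fleming type (section 6.6); threshold 0.05 for the primary P-value (section 6.3).

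**Step 1. Reproduce the plan's sample size.** With the formula in section 6.5 and an average rate of 0.45:

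n = [1.960·√(2·0.45·0.55) + 1.282·√(0.21 + 0.24)]² / 0.30² = [1.379 + 0.860]² / 0.09 = 55.7, so 56 per group. This matches the protocol. It is a fixed-sample calculation at the full 0.05, with no allowance for the look.

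**Step 2. Boundaries that keep the total at 5%.** Let Z₁ and Z₂ be the interim and final statistics, bivariate normal with correlation √0.5 under no effect. The overall two-sided error is

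1 − P(|Z₁| < c₁ and |Z₂| < c₂).

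- *Spending function.* The error spent per side at the look is 2[1 − Φ(2.2414/√0.5)] = 0.00153. That gives c₁ = 2.963 (P < 0.0031). Solving for a total of 0.05 gives c₂ = 1.969 (P < 0.0490).
- *Classical boundary.* Setting c₁ = c₂/√0.5 and solving for a total of 0.05 gives c₁ = 2.797 (P < 0.0052) and c₂ = 1.977 (P < 0.0480).

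**Step 3. Overall error if the final test uses 0.05 (c₂ = 1.960).**

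| Boundary at the look | Final level for a total of 5% | Overall error with final P < 0.05 |
|---|---|---|
| Spending function | 0.0490 | 5.10% |
| Classical | 0.0480 | 5.20% |

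A simulation of 4 million pairs (Z₁, Z₂) gave 5.12% and 5.21%. Applying the spending function directly to a two-sided 0.05, instead of 0.025 on each side, gives interim 0.0056, final 0.0478 and overall error 5.22%. If the look falls anywhere from 40% to 60% of information, the two forms in the table give 5.03% to 5.35%.

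**Step 4. Cost of the lower threshold.** For the final test alone at 65 per group,

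power = Φ{[0.30·√65 − c₂·√0.495] / √0.45}.

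- c₂ = 1.960: Φ(1.550) = 93.9%
- c₂ = 1.969: Φ(1.541) = 93.8%
- c₂ = 1.977: Φ(1.532) = 93.7%

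The formula in Step 1 then needs 56 (final level 0.0490) or 57 (0.0480) per group, still below 65.

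**The case against.** The strongest reply is that the 0.05 in section 6.3 is the same trial-level figure as in the synopsis and section 6.5. A spending function allocates a total across all looks, including the last, so section 6.6 already implies a final boundary below 0.05. On that reading the sections are compatible and only a cross-reference is missing. This largely stands: the protocol does plan control of the error rate. But section 6.3 attaches 0.05 directly to the primary P-value, and nothing tells the analyst to read it as an overall level.

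Three further replies also have weight.

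- **Boundary numbers are often left to the SAP or the DSMB's documents.** Agreed. Their absence alone is not a fault. The fault is that the one number the protocol does fix disagrees with the design it adopts.
- **The figures rest on a normal approximation.** The actual test is a stratified test on binary data. Simulated null trials with seven near-equal clinics (an assumption) and null rates of 0.30 and 0.40 gave about 5.0% to 5.2% without continuity correction and just over 3% with it. The protocol does not say whether a correction is used.
- **The bounds are called guidelines.** If a crossed bound led to neither a stop nor an efficacy claim, the excess would be smaller.

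A reader might therefore infer that the trial's real error rate definitely exceeds 5%, or that it has no alpha control. The documents support neither: the first depends on test details the protocol leaves open, and the second is contradicted by section 6.6.

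**Conclusion.** The point holds as an unreconciled threshold. Taken literally at the final analysis, section 6.3 uses a cut-off 0.001 to 0.002 too lenient for the design in section 6.6, and the nominal overall error is about 5.1% to 5.2% instead of 5%. These figures assume a look at 50% information, symmetric two-sided bounds that are acted on, and normal test statistics. The practical consequence is confined to a final P between about 0.048 and 0.050. Severity is minor, but the ambiguity bears on the primary conclusion and should be removed before any unmasked efficacy data are reviewed.

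**What to change.** - **Section 6.3.** Replace the threshold sentence with a statement that 0.05 is the overall two-sided level for the primary comparison, and that the final Mantel-Haenszel P-value is judged against the final O'Brien-Fleming boundary from section 6.6, computed at the information fraction actually reached at the interim.
- **Section 6.6.** Name the boundary form and give both nominal levels. At 50% information these are about 0.0031 interim and 0.0490 final for the spending function that section 6.6 names, or 0.0052 and 0.0480 if the classical boundary is meant. Only the trial team can say which was intended.

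The cost is two sentences. The planned 65 per group stays, and power for the final test goes from 93.9% to 93.8% or 93.7%.

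### Covariate adjustment waits for suspected confounding and unnamed covariates, when it should rest on baseline GCSI named in advance and always run

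*Protocol*

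**What the plan says.** Protocol 6.3 sets the primary analysis: "P-values will be derived from the Mantel-Haenszel" chi-squared test, stratified by clinic, comparing the proportions improved. Clinic is also the randomization stratum (3.2). Baseline GCSI is neither a stratum nor a covariate, although the response in 6.2 is a fall of at least 50% from the patient's own baseline score.

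Adjusted models are conditional. Section 6.3 considers confounding unlikely because the trial is randomized and large enough, and then provides for adjusted models: "if confounding should occur, sensitivity analyses using logistic regression models with GCSI score improvement as the binary response and treatment group indicator". Whichever confounders are suspected at that point join the model. The section adds that the Mantel-Haenszel P-value remains the primary one.

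For the secondary hypotheses other than the two subgroup hypotheses and dose escalation, 6.3 names Mantel-Haenszel tests for binary outcomes and Wilcoxon rank sum tests for numerical changes. It continues: "If concerns about confounding arise, logistic regression models for improvement outcomes and linear regression models for numerical change outcomes will be used". The stated purpose is correction, but nothing here says which P-value is then reported.

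**The concern.** Randomization makes the unadjusted comparison valid. Any baseline difference between the arms is chance, so confounding in the observational sense is not what should decide whether to adjust. The sound reason is that a covariate predicts the outcome, which can be judged before unmasking. Baseline GCSI is the obvious candidate: it is required for entry, recorded for everyone (Appendix 9.2), and is the same scale as the outcome.

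The protocol ties adjustment to suspicion instead. It gives no threshold, no decision-maker and no covariate. Two things are at stake:

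- Some power is forgone if baseline GCSI predicts response.
- The decision to adjust, and the covariates used, may be settled with results in view. For the secondary outcomes, which carry no multiplicity adjustment, this leaves two candidate P-values per test and no rule between them.

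**Working it through.** **1. The plan's own figure.** Protocol 6.5 assumes "0.6 in the nortriptyline group compared to 0.3 in the placebo group", two-sided alpha 0.05 and 90% power. The average proportion is 0.45, so the printed formula gives

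n = [1.960 × √(2 × 0.45 × 0.55) + 1.282 × √(0.30 × 0.70 + 0.60 × 0.40)]² / 0.30² = (1.379 + 0.860)² / 0.09 = 55.7, rounded up to 56.

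This agrees with "The number per group, using the above formula is 56 for a total of 112". At the planned 65 per group:

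- 0.60 v 0.30: z = (√65 × 0.30 − 1.379) / 0.671 = 1.55, power 93.9%.
- 0.50 v 0.30: z = (√65 × 0.20 − 1.358) / 0.678 = 0.375, power 64.6%.

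**2. How often a trigger could be pulled.** With 65 per arm, the standardized baseline difference has standard error √(2/65) = 0.175. Chance alone gives a difference above 0.2 SD in about 25% of trials and above 0.25 SD in about 15%, for one covariate. With several covariates in view, finding one to suspect is easy.

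**3. Does a relative 50% cut already deal with baseline?** Write follow-up GCSI as F = a + bB + e, where B is baseline. Response means F ≤ 0.5B, that is, a + (b − 0.5)B + e ≤ 0. Baseline drops out only when b = 0.5. The documents do not give b, so it is an assumption. Baseline was simulated as normal, restricted to 21 to 45 (SD 4.4 to 5.6 after the cut-off), with residual SD 7 to 9 and a 30% response rate:

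| Slope b | Odds ratio for response per SD of baseline |
|---|---|
| 0 | 1.50 to 1.96 |
| 0.25 | 1.23 to 1.39 |
| 0.5 | 1.00 to 1.01 |
| 0.75 | 0.71 to 0.81 |
| 1.0 | 0.51 to 0.66 |

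For slopes of 0 to 1 the association therefore lies between none and about 2 per SD, in either direction (1/0.51 = 1.96).

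**4. Power with and without baseline.** Simulation of 130 patients in 7 clinics, 4,000 trials per setting. It compares clinic-stratified Mantel-Haenszel with conditional logistic regression stratified by clinic and adjusted for baseline:

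| Response rates | OR per SD (assumed) | Mantel-Haenszel | Adjusted | Change (points) |
|---|---|---|---|---|
| 0.60 v 0.30 | 1.0 | 93.5% | 93.4% | −0.1 |
| 0.60 v 0.30 | 1.65 | 94.0% | 95.2% | +1.2 |
| 0.60 v 0.30 | 2.0 | 93.6% | 95.7% | +2.1 |
| 0.50 v 0.30 | 1.0 | 64.6% | 65.6% | +1.0 |
| 0.50 v 0.30 | 1.65 | 63.9% | 67.8% | +3.9 |
| 0.50 v 0.30 | 2.0 | 64.7% | 69.8% | +5.1 |

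The Monte Carlo standard error of one power figure is √(0.94 × 0.06/4000) = 0.4 points in the upper rows and √(0.65 × 0.35/4000) = 0.8 points in the lower rows. The +1.0 where there is no association is therefore compatible with no gain. A further simulation over slopes of 0 to 1.2 gave gains of about 0 to 4 points at 0.60 v 0.30 and about 0 to 8 points at 0.50 v 0.30.

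**5. Type I error.** The clinic-stratified, baseline-adjusted test rejected a true null in 4.6 to 5.6% of trials, against 4.4 to 5.6% for Mantel-Haenszel. Ordinary logistic score tests with seven clinic terms and baseline ran at 5.2 to 6.4%, against 4.7 to 5.4% for Mantel-Haenszel (Monte Carlo error about 0.35 points). Without baseline they ran at 5.3 to 6.0%, so the excess comes with the clinic terms and not with the baseline score.

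**The case against.** The strongest reply is that nothing here is an error. The test, its strata and the reported primary P-value are all fixed, and the strata match the randomization. This stands. A reader might infer that covariates picked afterwards could change the primary conclusion. They cannot, because 6.3 keeps the Mantel-Haenszel P-value primary in all cases.

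A reader might also infer that the primary analysis ignores baseline GCSI, or that the trial is short of power without adjustment. Neither is supported. Baseline scales the response, the entry cut-off of 21 narrows its range, and 65 per group gives 93.9% power at the protocol's own effect. A material loss of power cannot be shown from the documents, since they give no slope.

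Nor is adjustment free. A logistic model gives a conditional odds ratio, whereas the trial was sized on a difference in proportions, and ordinary clinic terms loosen the test slightly. The second point concerns that form of model and not a properly stratified one.

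Finally, covariate lists are commonly left to the analysis plan, which is not shown. Their absence alone would be no finding. The trigger, however, is stated in the protocol, and it puts adjustment on the wrong basis. The protocol's promise to interpret secondary findings cautiously does not say which P-value is to be interpreted.

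**Conclusion.** The point holds as a modest matter of efficiency and pre-specification, not as a flaw in the validity of the primary test. Adjustment should follow prognostic value declared in advance, and the protocol ties it to suspected confounding with open covariates. This affects the sensitivity and secondary analyses only.

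The power at stake on the primary comparison is about 0 to 4 points at the design effect, about 0 to 8 points if the true rates are 0.50 v 0.30, and nil at a slope of 0.5. The upper ends need an association at the strong end of what was assumed. These figures rest on assumed slopes, baseline spread and residual spread. The case for pre-specification does not depend on them. The smaller effect is worth showing because 6.5 rests the 30-point difference on expert opinion and adds patients for possible mis-specification of the rates.

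**What to change.** - Name baseline GCSI in 6.3 and run, in all cases, a clinic-stratified analysis of the primary outcome adjusted for it. Use conditional logistic regression, or a covariate-adjusted stratified test that keeps the comparison of proportions. Avoid ordinary logistic regression with a term per clinic.
- State its rank: either the primary analysis, or a fixed supporting analysis beside Mantel-Haenszel. If it becomes primary, the interim look in 6.6 and the final analysis should use the same test. The supporting role leaves the monitoring plan untouched.
- For secondary outcomes, adjust for the outcome's own baseline value where one is collected, for example GCSI subscores, SF-36, satiety volume and EGG (Appendix 9.2).
- Delete both confounding triggers, and state which P-value stands for each secondary outcome.
- Report response proportions by arm beside any conditional odds ratio.

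The cost is wording in the protocol or analysis plan before unmasking. No new data are needed. The small downside is the conditional odds ratio, which the reported proportions offset.

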#### **Major human polymorphic variant CYP2D6 alleles and their population distribution**

Major variant allele*	Mutation	Consequence	Allele Frequency (%)			
			Caucasians	Asians	Black Africans	Ethiopians and Saudi Arabians
CYP2D6*2xn	Gene duplication	Increased enzyme activity	1-5	0-2	2	10-16
CYP2D6*4	Defective splicing	Inactive enzyme	12-21	1	2	1-4
CYP2D6*5	Gene deletion	No enzyme	2-7	6	4	1-3
CYP2D6*10	P34S, S486T	Unstable enzyme	1-2	51	6	3-9
CYP2D6*17	T1071,R296C, S486T	Altered affinity for substrates	0	0	20-35	3-9

\*All variant alleles are listed by the Human CYP Allele Nomenclature Committee at <http://www.imm.ki.se/cypalleles/cyp2d6.htm>

Individuals with multiple active gene copies metabolize drugs more rapidly, whereas individuals lacking functional CYP2D6 genes metabolize at a lower rate. Nortriptyline is metabolized by CYP2D6. The activity of CYP2D6 can markedly affect nortriptyline levels and efficacy. These polymorphisms may require a change in the dose from 28-180% of the usual dose to achieve similar results. There is also some evidence that nortriptyline can also be metabolized to a small extent through CYP3A4 and 2C19.

Correlating the CYP2D6 status of an individual to their clinical response will provide important information on whether there is need to individualize nortriptyline dosages according to CYP2D6 status to achieve therapeutic benefit.

[figure not shown]

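### The interaction test prescribed for nortriptyline blood levels is not estimable, and the contrasts that remain compare groups formed after randomisation

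*Protocol*

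**What the plan says.** The second secondary hypothesis in Protocol 6.1 concerns patients with higher nortriptyline levels during follow-up, who "will experience a better response compared to placebo and compared to patients with lower blood levels of nortriptyline". It therefore contains two contrasts: high level against placebo, and high level against low level.

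Section 6.3 treats this hypothesis together with the pharmacogenetic one, as differential effects in "subgroups of patients defined by pharmacogenetic profiles and adherence levels (nortriptyline blood levels), respectively". One logistic model serves both. It has random clinic effects, and "fixed effects for treatment group, subgroup indicator variables, and treatment group by subgroup interaction effects will be used". The evidence "will be considered statistically significant if the P-value for the interaction terms is <0.01". No other model is given for blood levels.

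On the grouping, 6.3 states: "The profiles and blood level cut offs will not be pre-defined, but will be made on the basis of the best available information". The following paragraph adds: "No adjustments for multiple comparisons will be applied to the secondary hypotheses, which are pre-specified". It also promises that significant findings will be read with caution.

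Section 2.7 says of the same levels: "The activity of CYP2D6 can markedly affect nortriptyline levels and efficacy".

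**The concern.** A treatment-by-subgroup interaction asks whether the treatment effect differs between kinds of patient, and each kind must exist in both arms. Genotype meets that condition. A nortriptyline level during follow-up does not: placebo patients take no nortriptyline (5.7), and 4.4 bars other tricyclics during the trial. The high-level group can therefore contain only nortriptyline patients.

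Software may drop the redundant term and still print a P-value. That value could then be reported under the 0.01 rule as evidence of a differential treatment effect. It would in fact be a high-versus-low comparison among treated patients, open to confounding. The relation of blood level to response is one of the five objectives in section 1, so the wording matters although the hypothesis is secondary.

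**Working it through.** **The plan's own figure.** The protocol gives no power or sample size for the blood-level analysis. The only related figure is the primary sample size in 6.5, with response 0.30 versus 0.60, two-sided 0.05 and 90% power:

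n = [1.960·√(2·0.45·0.55) + 1.282·√(0.30·0.70 + 0.60·0.40)]² / 0.30² = (1.379 + 0.860)² / 0.09 ≈ 55.7, so 56 per group. This reproduces the protocol. The planned 65 per group is used below.

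**Step 1: is the interaction estimable?** The columns are intercept, treatment T, high level H and T×H. With placebo coded as low (level zero), only three distinct rows occur:

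| Group | 1 | T | H | T×H |
|---|---|---|---|---|
| Placebo | 1 | 0 | 0 | 0 |
| Nortriptyline, low | 1 | 1 | 0 | 0 |
| Nortriptyline, high | 1 | 1 | 1 | 1 |

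H equals T×H for every patient, so the rank is 3 of 4. The other codings do not help:

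- Placebo levels set to missing: 65 patients, rank 2 of 4, and the treatment effect is lost as well.
- Tertiles: rank 4 of 6.
- The same model with a two-class genotype present in both arms: rank 4 of 4.

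**Step 2: what can be estimated?** High versus placebo is row 3 minus row 1, (0,1,1,1). High versus low is row 3 minus row 2, (0,0,1,1). Both are estimable. The interaction alone, (0,0,0,1), is not a combination of the rows. A three-group factor (placebo, low, high) has 3 columns and rank 3, but contains no interaction to test.

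**Step 3: are those contrasts randomised?** Follow-up plasma is drawn at weeks 12 and 15 (5.6). By then the dose may have been reduced or stopped for tolerability (3.4), and the level also depends on CYP2D6 (2.7). Patients who stop remain in scheduled follow-up (3.4, 5.12) and would tend to fall in the low group. The binary outcome in 6.2 can be met at weeks 3 and 6, before the first follow-up sample. Membership of the high group is therefore a post-randomisation event.

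The possible size was simulated with no drug effect, 65 patients, a median split, nominal 0.01 and 10,000 replicates. The correlation between a prognostic factor and level, and the log-odds of response per SD of that factor, are assumptions, not trial figures:

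| Correlation | Log-odds per SD | High | Low | False-positive rate |
|---|---|---|---|---|
| 0 | 1.0 | 33% | 33% | 0.011 |
| 0.3 | 0.7 | 35% | 29% | 0.024 |
| 0.3 | 1.0 | 37% | 29% | 0.036 |
| 0.5 | 1.0 | 41% | 26% | 0.093 |

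With no drug effect, placebo would have the arm's overall rate, about 32% to 33%. The high group would then look about 3 points (35 − 32) to 7 points (40.6 − 33.1) better than placebo.

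**Step 4: cut-offs chosen after the data.** Take 65 nortriptyline patients ordered by level, with no true association. For a cut after patient k, z = (p_high − p_low) / √[p(1 − p)(1/k + 1/(65 − k))], rejecting if |z| > 2.576 at any candidate cut. Results from 20,000 replicates, for response rates 0.30 and 0.60:

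| Candidate cuts | True error at nominal 0.01 |
|---|---|
| One fixed (median) | 0.010 to 0.011 |
| Best of three (tertiles, median) | 0.023 to 0.024 |
| Best in middle 50% | 0.068 to 0.071 |
| Best in middle 80% | 0.109 |

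**Step 5: power of the surviving high-versus-low contrast.** With a median split of 65 and two-sided 0.01, power is 17% for 70% versus 50%, 46% for 75% versus 45%, and 78% for 80% versus 40%. Each pair averages the 60% assumed in 6.5.

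**The case against.** The strongest reply is that only one redundant column is lost. A reader might infer that the model cannot be fitted at all, or that the objective yields no result. The protocol does not support that: once the duplicate is dropped, both contrasts in the hypothesis can be estimated, and the objective in section 1 asks only whether levels correlate with response to nortriptyline. This stands. The missing piece is the interaction test, to which 6.3 attaches its significance rule.

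A reader might also infer that placebo patients are not sampled, or that only patients still on drug are. Neither follows. Plasma banking is scheduled without regard to arm (5.6, Appendix 9.2), and patients who stop stay in follow-up. Placebo values would be zero or undetectable, and the aliasing is the same.

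A third tempting inference is that cut-offs will be picked by searching the outcome. The wording permits this but does not prescribe it; best available information may mean outside evidence. The 0.109 is a worst case. An SAP, which is not at hand, could fix the cut-offs before unmasking, although it would have to depart from the protocol's statement that they are not pre-defined.

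The 0.01 threshold and the promised caution help a little. They cannot supply a missing test or make the groups randomised. Calling the hypotheses pre-specified is defensible for their wording, less so for groups whose boundaries are left open. The label of adherence levels is a lesser matter: levels reflect both adherence and metabolism.

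**Conclusion.** The concern holds for the blood-level hypothesis only. The interaction test that 6.3 prescribes is not estimable, which follows from the design and needs no numerical assumption beyond placebo patients having no measurable nortriptyline. The estimable contrasts are not randomised treatment effects. Under the assumed confounding, a drug without effect could show a high-versus-low gap of about 6 to 15 points and a false-positive rate of 0.024 to 0.093 at nominal 0.01. Outcome-driven cut-offs, if used, would separately raise the nominal 0.01 to about 0.02 to 0.11; a cut-off fixed independently of outcome would not.

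The pharmacogenetic model has full rank, and treatment comparisons within a genotype remain randomised. The primary analysis and sample size are untouched. The correction should be made because the text prescribes a test that cannot be carried out and replacing it costs almost nothing.

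**What to change.** - **Pharmacogenetic hypothesis:** keep the interaction model and the 0.01 rule for CYP2D6 genotype, with metaboliser classes fixed before unmasking.
- **Blood-level hypothesis:** replace the interaction model in 6.3 with an exposure-response analysis within the nortriptyline arm, matching the objective in section 1. Enter level as a continuous variable on a scale that admits zero, because patients who have stopped may have none and a plain logarithm would be undefined. Alternatively, use groups with cut-offs fixed before unmasking. Adjust for baseline GCSI and clinic. Adjusting for dose is debatable, since dose determines level and is itself changed for tolerability.
- **Labelling:** call the blood-level result non-randomised and exploratory. In 6.1, either drop the comparison with placebo from this hypothesis or mark it as non-randomised.

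The cost is wording in 6.1 and 6.3. Plasma and GCSI are already collected at weeks 12 and 15, so no new data are needed. The downside is that the blood-level result becomes openly exploratory.
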